3.4.7 SPONSOR Responsibility for Reporting Adverse Experiences

All adverse experiences will be reported to regulatory agencies, IRB/IECs, and investigators in accordance with all applicable global laws and regulations.

3.4.8 Events of Clinical Interest

Selected non-serious and serious adverse events are also known as Events of Clinical Interest (ECI) and must be reported to the Sponsor.

For the time period beginning when the consent form is signed until treatment allocation/randomization, any ECI, or follow up to an ECI, that occurs to any subject must be reported within 24 hours to the Sponsor if it causes the subject to be excluded from the trial, or is the result of a protocol-specified intervention, including but not limited to washout or discontinuation of usual therapy, diet, placebo treatment or a procedure.

For the time period beginning at treatment allocation/randomization through 90 days following cessation of treatment, or 30 days following cessation of treatment if the subject initiates new anticancer therapy, whichever is earlier, any ECI, or follow up to an ECI, whether or not related to the Sponsor's product, must be reported within 24 hours to the Sponsor, either by electronic media or paper. Electronic reporting procedures can be found in the EDC data entry guidelines. Paper reporting procedures can be found in the Investigator Trial File Binder (or equivalent).

Events of clinical interest for this trial include:

1. An overdose of Sponsor's product, as defined in Section 3.4.3 and 3.4.3.1 - Definition of an Overdose for This Protocol and Reporting of Overdose to the Sponsor, that is not associated with clinical symptoms or abnormal laboratory results.
2. An elevated AST or ALT lab value that is greater than or equal to 3X the upper limit of normal and an elevated total bilirubin lab value that is greater than or equal to 2X the upper limit of normal and, at the same time, an alkaline phosphatase lab value that is less than 2X the upper limit of normal, as determined by way of protocol-specified laboratory testing or unscheduled laboratory testing.*

*Note: These criteria are based upon available regulatory guidance documents. The purpose of the criteria is to specify a threshold of abnormal hepatic tests that may require an additional evaluation for an underlying etiology. The trial site guidance for assessment and follow up of these criteria can be found in the Investigator Trial File Binder (or Administrative Binder, or equivalent).

All ECIs should be reported to the SPONSOR within 24 hours or, at least, on the following working day to the SPONSOR via facsimile (documentation is found in the Administrative Binder).

3.4.9 Protocol-Specific Exceptions to Serious Experience Reporting

Efficacy endpoints outlined in this section will not be reported to the Sponsor as described in Section 3.4.5. Immediate Reporting of Adverse Experiences to the Sponsor except as follows:

- If a serious and unexpected adverse experience occurs for which there is evidence suggesting a causal relationship between the drug and the event, the event must also be reported as a serious and unexpected suspected adverse reaction within 24 hours to the Clinical Monitor either by electronic media or paper even if it is a component of the study endpoint (e.g., all-cause mortality).

Specifically, the suspected/actual events (as opposed to endpoints or endpoint components) covered in this exception are as follows: hospitalization or death due to progression of the cancer under study if the events are considered drug related. Note: As described in Section 3.4.5.1, any secondary primary cancer needs to be reported as an SAE.

For this protocol, the Following MedDRA Preferred Terms are considered suspected efficacy endpoint/endpoint events:

- Disease Progression
- Malignant Neoplasm Progression

The Sponsor will monitor unblinded aggregated efficacy endpoint event and other safety data including fatal events to ensure the safety of the subjects in the trial. Any suspected endpoint which upon review is not progression of the cancer under study will be forwarded to global safety as a SAE within 24 hours of determination that the event is not progression of the cancer under study.

3.5 STATISTICAL ANALYSIS PLAN (SAP)

This section outlines the statistical analysis strategy and procedures for the study. If, after the study has begun, changes are made to primary, secondary or tertiary objectives and/or hypotheses, or to the statistical methods related to those objectives and/or hypotheses, then those changes, along with an explanation as to when and why they occurred, will be listed in the Clinical Study Report (CSR) for the study. Post hoc exploratory analyses will be clearly identified in the CSR. No separate Statistical Analysis Plan (SAP) will be issued for this study.

3.5.1 Responsibility for Analyses/In-House Blinding

The statistical analysis of the data obtained from this study will primarily be the responsibility of the Clinical Biostatistics department of the SPONSOR.

This trial is being conducted as an open-label study (i.e., patients, investigators, and SPONSOR personnel will be aware of patient treatment assignments after each patient is

enrolled and treatment is assigned). However, for those randomized cohorts, treatment assignment is based on an allocation schedule generated in-house to maintain randomness.

3.5.2 Hypotheses/Estimation

Objectives and hypotheses of the study are stated in Section 2.1.

The primary endpoint is RR based on RECIST 1.1 by blinded central reviewers for demonstrating the anti-tumor activity of pembrolizumab (MK-3475) in all populations (see hypotheses in Section 3.5.7). In addition, RR and DCR as assessed per irRC by investigators in the ipilimumab-naïve population treated at 10 mg/kg in Part B enrolled through Amendment 4 will be analyzed for internal decision purposes, and the study in this population is considered positive (i.e., demonstration of proof-of-concept) if the outcome in either endpoint is positive. The following table (Table 3-5) provides the target RR and DCR of interest for the ipilimumab-naïve population. The null hypothesis is derived from the published Phase III data on single agent ipilimumab [71], and the alternative hypothesis is derived from the nivolumab data as reported at the 2010 American Society of Clinical Oncology (ASCO) meeting [74]. To properly reflect the preliminary nature of the nivolumab data, two effect sizes are considered for the alternative hypothesis (intermediate and high), with the high effect size representing the data as reported and the intermediate effect size representing a slightly lower efficacy size that is still considered of clinical interest.

Table 3-5

Target Response Rate (RR) and Disease Control Rate (DCR) of Interest in Ipilimumab-naïve Population

Hypotheses	Week 12		Overall	
	RR	DCR	RR	DCR
Null hypothesis	5%	30%	10%	30%
Alternative hypothesis (intermediate)	15%	45%	25%	50%
Alternative hypothesis (high)	20%	50%	30%	55%

An important secondary objective of study is to investigate the correlation between various candidate biomarkers and anti-tumor activity of pembrolizumab (MK-3475). The primary biomarker hypothesis to be tested in the study is that expression of PD-L1 in tumor tissue at baseline is concordant with anti-tumor activity, assessed as maximum total reduction (%) in tumor volume produced by pembrolizumab (MK-3475).

3.5.3 Analysis Endpoints

3.5.3.1 Efficacy Endpoints

RR and DCR will serve as primary efficacy endpoints only for the ipilimumab-naïve population treated at 10 mg/kg in Part B enrolled through Amendment 4 for internal decision purposes, and the study in this population is considered positive (i.e., demonstration of proof-of-concept in this population) if the outcome in either endpoint is positive. The recently published immune-related response criteria (irRC) as assessed by investigators will be applied as primary measure for assessment of tumor response [18]. RR and DCR will be also assessed based on RECIST 1.1 by blinded central reviewers as supportive analyses. Interim analyses will be based on RR and DCR at Week 12. Confirmation is required for final analysis of RR, but not for the interim analyses. Secondary efficacy endpoints for the above population will include duration of response, progression-free survival (PFS) and overall survival (OS). Response duration will be only determined for confirmed responses and is defined as the time from first documentation of response to first documentation of disease progression or death. PFS will be measured from start of treatment to documentation of definitive disease progression or death due to any cause, whichever occurs first. OS is defined as time from treatment initiation to death due to any cause.

The primary endpoint is RR to further demonstrate the anti-tumor activity of pembrolizumab (MK-3475) in all populations except as noted above. The primary measure for assessment of tumor response is based on RECIST 1.1 by blinded central reviewers and the secondary measure is based on irRC by investigators. DCR, response duration and PFS based on both irRC and RECIST 1.1, and OS will serve as secondary endpoints.

3.5.3.2 Safety Endpoints

The primary safety endpoint in Part A of the study is DLT. Other safety measures evaluated in all parts of the study are all other adverse events, laboratory safety assessments, ECGs, and vital signs.

3.5.3.3 Pharmacokinetic (PK) and Pharmacodynamic Endpoints

Blood samples for serum levels of pembrolizumab (MK-3475) and analysis of target engagement will be obtained at the time points listed in the Study Flow Chart, Section 1.7.

As of Amendment 11, blood samples for serum levels of pembrolizumab (MK-3475) and analysis of target engagement will not be collected (see Section 3.3.2).

3.5.3.4 Predictive Biomarker Endpoints

The primary candidate biomarker to be investigated in this study is PD-L1 expression levels in tumor tissue at baseline, which will be assessed by IHC. Other candidate biomarkers which will be investigated include expression of PD-L2 and PD-1, RNA

signature profiles, and quantitative RNA expression of candidate genes of interest, including PD-L1.

3.5.4 Analysis Populations

3.5.4.1 Efficacy Analysis

The primary efficacy analyses will be based on the Full Analysis Set (FAS) population. Patients with measurable disease at baseline, which is defined separately under investigator evaluation and central review, who received at least one dose of study treatment will be included in the FAS population. Analyses of PFS and OS are based on the APaT population that consists of all patients who received at least 1 dose of study treatment.

3.5.4.2 Safety Analysis

The All Patients as Treated (APaT) population will be used for the analysis of safety data in this study. The APaT population consists of all patients who received at least 1 dose of study treatment.

In order for a patient to be considered evaluable for the analysis of DLT, the patient must have either had a DLT in Cycle 1 or had received at least 90% of the prescribed dose of pembrolizumab (MK-3475) in Cycle 1 and completed all safety evaluations up to and including at least 28 days after the first administration of pembrolizumab (MK-3475) without experiencing a DLT. A patient without a DLT will be replaced if he/she did not adequately complete the evaluation period associated with the first cycle of study therapy (i.e., discontinued prematurely due to a reason unrelated to study therapy) or if that patient received <90% of the prescribed dose.

3.5.4.3 Pharmacokinetic and Pharmacodynamic Analyses

Pharmacokinetic and pharmacodynamic analyses populations are defined separately for each parameter of interest, and include all evaluable patients for each. Factors such as age group and gender will also be explored.

As of Amendment 11, pharmacokinetic and pharmacodynamic analyses will not be performed (see Section 3.3.2).

3.5.4.4 Predictive Biomarker Analyses

The primary predictive biomarker analyses are based on evaluable patients with both a valid PD-L1 expression measurement and at least one disease assessment post-treatment. Patients with MEL will be evaluated separately from patients with NSCLC. Different cutoff points may be applied to different tumor types.

Exploratory analyses of other candidate predictive biomarkers will be conducted similarly.

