The randomization of the 250 2L+ patients may be stratified by PD-L1 expression level based on a preliminary cutoff point once available, mainly based on Part C data. Data based on the patients enrolled in the non-randomized portions of Part F (Amendment 06) will be pooled with Part C data, some data from Part A, and possibly data from 1L patients in Part F (Amendment 06), to determine the final cutoff point for patients with strongly positive tumors (the primary population in this cohort) using the same estimation methods as for the melanoma patients. Just like for the melanoma patients, the cutoff point is determined in isolation to the 250 patients enrolled in the randomized portion of Part F (Amendments 07 and 08) to ensure that the subgroup analysis of the patients with strongly positive tumors is blinded to the determination process. Notice that the cutoff point is driven by patients on the Q3W schedule. To properly compare the difference (if any) in cutoff point between the two dose schedules, patients treated at 10 mg/kg Q2W will be divided into two sets with half in the training set and half in the validation set for estimation and validation of a cutoff point specifically for the Q2W schedule.

Enrollment of patients with weakly positive tumors will be capped at 50%. Besides, an interim analysis will be conducted to potentially exclude patients with weakly positive tumors (based on final cutoff point) from further enrollment (see Section 3.5.9 for details). Regardless, the final cutoff point, once determined, won't be changed for the primary analysis purposes to maintain the integrity of the analysis.

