In addition to detecting dose response, we are also interested in testing whether pembrolizumab (MK-3475) is superior to putative chemotherapies in this population. While the spontaneous RR is likely less than 5%, there is no historical data on response rate of chemotherapies in the ipilimumab-refractory population. However, it ranged from 5% to 10% for chemotherapies in three recently completed phase 3 studies (ipilimumab in 1st line melanoma patient, and trametinib and vemurafenib in patients with BRAF V600E mutation). Therefore, it is reasonable to use 10% as the null hypothesis for testing the anti-tumor activity of pembrolizumab (MK-3475) against putative chemotherapies in this population. With 80 patients treated at a dose level, the study has 93% power to reject the null hypothesis at a type I error rate of 2.5% (one-sided) when the true response rate of pembrolizumab (MK-3475) is 25%. A p-value of 2.5% approximately corresponds to a 19% empirical response rate when sample size is 80. With the prevalence of high PD-L1 projected to be from 40% to 60%, the number of high PD-L1 patients treated at a dose level ranges from 32 to 48 and the half-width of the 95% confidence intervals for RR at a dose level approximately ranges from 14% to 17% when the empirical RR in the high PD-L1 group is 50% and from 13% to 16% when the empirical RR in the high PD-L1 group is 70% or is 30%. With 32 to 48 patients in the PD-L1 high group, the study has 79% to 94% power to reject the null hypothesis of 10% RR at type I error rate of 2.5% (one-sided) when the true RR is 30%.

Part C NSCLC (single arm)

With 35 NSCLC patients treated at RP2D, the study has approximately 80% power to rule out a $\leq 9\%$ RR (null hypothesis) when the true RR is 22% at the 10% type I error rate (one-sided).

Part D ipilimumab-naïve enrolled after Amendment 04 (randomized)

With 44 patients treated at 2 mg/kg and 44 treated at 10 mg/kg, the study has 80% power to detect 30% vs. 10% or 90% power to detect 25% vs 5% in RR between the two dose levels at the 10% type I error rate (one-sided). A p-value of 10% approximately corresponds to a 12% empirical difference in RR.

With 44 patients treated at a dose level, the study has 89% power to test the null hypothesis of RR=10% at 2.5% type I error rate (one-sided) when the true RR is 30%. A p-value of 2.5% approximately corresponds to an empirical RR of 23% (10/44).

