Based on preliminary data from the non-randomized patients, the RR appears similar between the ipilimumab-refractory population and the ipilimumab-naïve population. A pooled analysis of the PD-L1 high patients from Part B (randomized) and Part D (randomized) will be conducted. It is expected that 50 to 75 PD-L1 high patients will be treated at a dose level in the pooled analysis. With this sample size, the study has >95%

power to reject the null hypothesis of 10% RR at type I error rate of 2.5% (one-sided) when the true RR is 30%.

Part B enrolled after Amendment 04 (randomized: 10 mg/kg Q3W vs 10 mg/kg Q2W)

A total of approximately 230 patients will be randomized 1:1 to 10 mg/kg Q3W or 10 mg/kg Q2W, stratified by ipilimumab-naïve vs non ipilimumab-naïve. Based on preliminary data from non-randomized patients, the RR appears similar between the non ipilimumab-naïve population and the ipilimumab-naïve population. The primary analysis of this cohort is based on a pooled analysis, stratified by ipilimumab treatment history. Subgroup analyses will also be conducted. With 230 patients, the study has ~85% power to detect a 20% difference (i.e., 30% vs 50%) in RR between the two doses at the 2.5% type I error rate (one-sided). A p-value of 2.5% approximately corresponds to a 13% empirical difference in RR.

Similar to randomized cohorts in Part B and Part D between 10 mg/kg Q3W vs 2 mg/kg Q3W, anti-tumor activities of pembrolizumab (MK-3475) at a dose schedule as well as related to PD-L1 expression will also be investigated.

Part F NSCLC 1L PD-L1 positive (randomized)

With 44 patients per dose level, the study has 86% power to detect a 25% difference in RR (i.e., 45% vs 20%) at $\alpha=10\%$ (1-sided) between two dose levels. A p-value of 10% approximately corresponds to a 13% empirical difference in RR.

With 44 1L patients treated at a dose level, the study has 91% power to test the null hypothesis of $RR=25\%$ at 2.5% type I error rate (one-sided) when the true RR is 50%. A p-value of 2.5% approximately corresponds to an empirical RR of 41% (18/44).

Part F NSCLC 3L+ (single arm)

With 32 3L+ patients treated at 10 mg/kg, the study has 90% power to test the null hypothesis of $RR=10\%$ at 2.5% type I error rate (one-sided) when the true RR is 35%. A p-value of 2.5% approximately corresponds to an empirical RR of 25% (8/32).

Part F NSCLC 3L+ PD-L1 negative (single arm)

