With 40 patients treated at 10 mg/kg Q2W, the study has >90% power to rule out a >30% RR if <8 patients respond (i.e., probability of observing < 8 responses is <10% when true RR is 30%).

Part F NSCLC 2L+ PD-L1 positive (single arm)

With 40 patients treated at 2 mg/kg Q3W, the study has ~90% power to test the null hypothesis of RR =10% at 2.5% type I error rate (one-sided) when the true RR is 30%. A p-value of 2.5% approximately corresponds to an empirical RR of 22.5% (9/40).

Part F NSCLC 2L+ PD-L1 positive (randomized)

Approximately 250 patients will be randomized (3:2) to 10 mg/kg Q3W and 10 mg/kg Q2W. The randomization may be stratified by PD-L1 expression level based on a preliminary cutoff point once available (see Section 3.5.5.4 for details). With 250 patients, the study has approximately 95% power to detect a 15% difference in RR between the two doses at type I error rate of 10% (one-sided) assuming that the RR at 10 mg/kg Q3W is 10%.

Enrollment of patients with weakly positive tumors will be capped at 50% so that at least 75 patients with strongly positive tumors will be treated at 10 mg/kg Q3W. With 75 patients treated at 10 mg/kg Q3W, the study has 85% power to detect a 15% difference in RR between pembrolizumab (MK-3475) and historical control which is conservatively estimated to be 15% (i.e., 30% vs 15%) at type I error rate of 2.5% (one-sided). A p-value of 2.5% approximately corresponds to an empirical RR of 25% (i.e., the lower bound of the 95% CI for an empirical RR at 25% will exclude 15%). With 50 patients at 10 mg/kg Q2W, the study has 68% (or 89%) power to detect a 15% (or 20%) difference in RR between pembrolizumab (MK-3475) and historical control at type I error rate of 2.5% (one-sided). A p-value of 2.5% approximately corresponds to an empirical RR of 28% (i.e., the lower bound of the 95% CI for an empirical RR at 28% will exclude 15%). If 10 mg/kg Q2W has comparable anti-tumor effect to 10 mg/kg Q3W in the population, the two doses will be pooled for a joint analysis as appropriate. Regardless, if the primary analysis in the biomarker strongly positive population is positive a step-down analysis will be performed to assess all biomarker positive patients including patients with weakly positive tumors.

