3.5.9 Interim Analyses

Part B Ipilimumab-Naïve Patients (non-randomized)

The study will have two planned interim analyses for internal decision purpose in ipilimumab-naïve patients treated at 10 mg/kg in Part B enrolled through Amendment 4 (non-randomized). The endpoints in these interim analyses are RR and DCR at week 12. There is no intention to stop the trial for efficacy at the first or second interim analysis. The accrual for Part B is expected to be fast. Should it be slower than expected, one additional interim analysis may be added. The decision rules at the interim analyses serve as guidance and are non-binding. In absence of a control arm, outcomes in this single arm study have to be interpreted with caution, both at interim and final analyses.

The first planned interim analysis will occur when the first 11 patients are evaluable for response assessment at 12 weeks (i.e., have either completed the first tumor re-assessment at week 12 or discontinued the study before week 12). To prevent undue over-enrollment in case the futility bar will be crossed and the study may get terminated early, enrollment of the first 13 MEL patients in Part B will be restricted to ipilimumab-naïve patients.

The futility bar has been set at zero objective response in 11 evaluable patients AND disease control in <5 patients at week 12. This decision criterion has 51% power to rule out the null hypothesis, 89% power to rule out the intermediate effect size and 95% power to rule out the high effect size.

Enrollment will not be stopped for purpose of the first interim futility analysis. Accordingly, approximately 30-38 patients may have been enrolled when the data from that analysis will become available, based on current accrual rate projections. This will include patients without and with prior treatment with ipilimumab.

If the futility bar will be crossed at the first futility analysis (i.e., in case of $\geq 1/11$ responses OR $\geq 5/11$ patients with disease control), enrollment will continue to the

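### Section 3.5.4.4 does not say whether response and disease control rates by PD-L1 category keep treated patients who never had a post-treatment scan

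*Combined protocol and SAP*

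**What the plan says.** **The biomarker population.** Section 3.5.4.4 reads: "The primary predictive biomarker analyses are based on evaluable patients with both a valid PD-L1 expression measurement and at least one disease assessment post-treatment". It makes no exception for any endpoint.

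**What falls under it.** Section 3.5.5.4 sets out two steps for the primary biomarker hypothesis in melanoma: estimate a PD-L1 cutoff, then validate it. Under validation it compares RR, DCR and the other efficacy endpoints above and below the cutoff and fits a logistic model. It names no population there. For previously treated NSCLC, the same section refers to the final cutoff for "patients with strongly positive tumors (the primary population in this cohort) using the same estimation methods as for the melanoma patients".

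**The efficacy population.** Under Section 3.5.4.1, patients with measurable baseline disease "who received at least one dose of study treatment will be included in the FAS population". No post-treatment scan is required.

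**The sizing.** Section 3.5.7 counts treated patients for RR in PD-L1 groups. For ipilimumab-refractory melanoma, "the number of high PD-L1 patients treated at a dose level ranges from 32 to 48". For Parts B and D together, "It is expected that 50 to 75 PD-L1 high patients will be treated at a dose level in the pooled analysis". For previously treated NSCLC, "at least 75 patients with strongly positive tumors will be treated at 10 mg/kg Q3W". The Kendall tau sizing in the same section counts patients who have both a post-treatment assessment and a PD-L1 value.

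**Patients without a scan.** Section 3.5.5.4 expects some and gives them the lowest ranks, but only in a supportive Kendall analysis. Its other missing-data rule concerns indeterminate PD-L1 results. Neither rule covers RR or DCR by category.

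**The concern.** A treated patient who dies, progresses clinically or leaves before the first scan cannot be a documented responder. In the FAS that patient counts as a failure; under the literal text of Section 3.5.4.4 the patient disappears. Two analysts could follow the SAP and report different response rates for the same PD-L1 group.

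The excluded patients are all non-responders, so RR within a category can only rise. The comparison of high with low PD-L1 depends on which category loses more patients, so its bias has no fixed sign.

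More would be at stake if the same denominator reached the single-arm tests in PD-L1-high patients. The strongly positive NSCLC test serves the fifth primary objective in Section 2.1.1, and it also opens further testing: "if the primary analysis in the biomarker strongly positive population is positive a step-down analysis will be performed to assess all biomarker positive patients".

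**Working it through.** **1. Which denominator did the sizing use?**
- Refractory melanoma: 80 per dose x 40% to 60% PD-L1 high = 32 to 48.
- Pooled Parts B and D: (80 + 44) x 40% to 60% = 49.6 to 74.4; the SAP gives 50 to 75.
- NSCLC strongly positive: 250 x 3/5 x 50% = 75 on Q3W, and 250 x 2/5 x 50% = 50 on Q2W.

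These are full treated counts, with no allowance for missing scans.

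**2. The plan's power figures.** Take c as the smallest count whose exact one-sided binomial p-value against the null RR is at most 0.025.

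| Treated n | Null vs true RR | c | Exact level | Power | SAP |
|---|---|---|---|---|---|
| 32 | 10% vs 30% | 8 | 1.2% | 78.8% | 79% |
| 48 | 10% vs 30% | 10 | 1.9% | 94.3% | 94% |
| 50 | 10% vs 30% | 10 | 2.5% | 96.0% | >95% |
| 75 | 10% vs 30% | 14 | 1.6% | 99.1% | >95% |
| 50 | 15% vs 30% | 14 | 1.3% | 67.2% | 68% |
| 75 | 15% vs 30% | 19 | 1.3% | 84.3% | 85% |

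The RR figures reproduce on treated counts. The Kendall figure reproduces on scanned counts. Concordance odds of 2 give tau = (2-1)/(2+1) = 1/3. With n = 45 the null standard error is sqrt(2(2n+5)/(9n(n-1))) = 0.103, and power is 89.8% against the stated value of about 90%. So the SAP's own sizing uses one denominator for RR and another for tau.

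**3. Effect on RR in one category.** Let f be the unscanned share. Observed RR = true RR/(1-f). The documents give no f, so 5% to 20% is assumed. For a true RR of 30%:
- f = 5%: 0.30/0.95 = 31.6%
- f = 10%: 0.30/0.90 = 33.3%
- f = 20%: 0.30/0.80 = 37.5%

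**4. Effect on high versus low.** The RR ratio is multiplied by (1-f_low)/(1-f_high).
- f_high = 20%, f_low = 10%: 0.90/0.80 = 1.125, overstated.
- f_high = 10%, f_low = 20%: 0.80/0.90 = 0.889, understated.
- Equal losses leave the ratio unchanged.

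**5. If the PD-L1-high tests used scanned patients only.** The number scanned is m ~ Bin(n, 1-f), and responders are Bin(m, p0/(1-f)). The exact test at 2.5% one-sided is applied to m. The true RR among all treated equals the null p0. Type I error:

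| Test | All treated | f = 5% | 10% | 15% | 20% |
|---|---|---|---|---|---|
| 32 vs 10% | 1.2% | 1.6% | 2.5% | 3.2% | 4.0% |
| 48 vs 10% | 1.9% | 2.0% | 3.1% | 4.2% | 5.4% |
| 50 vs 10% | 2.5% | 2.5% | 3.0% | 4.3% | 5.7% |
| 75 vs 10% | 1.6% | 2.4% | 3.6% | 5.2% | 7.3% |
| 50 vs 15% | 1.3% | 2.4% | 3.4% | 5.1% | 7.6% |
| 75 vs 15% | 1.3% | 2.9% | 4.6% | 6.9% | 9.8% |

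At f = 5% only the last test passes 2.5%; 50 vs 10% stands at 2.48%. At f = 10%, 32 vs 10% is still within it, at 2.47%.

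**6. At the margin.** Against 15%, 18 of 75 gives p = 0.0268. Dropping one unscanned patient gives 18 of 74 and p = 0.0236. With 11 dropped, 16 of 75 (p = 0.089) becomes 16 of 64 (p = 0.0248).

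**The case against.** The strongest defense is that Section 3.5.4.4 was written for the Kendall analysis. Section 3.5.2 defines the primary biomarker hypothesis as concordance with tumor volume reduction, Section 3.5.6 gives that hypothesis its own error rate, and the tau sizing uses nearly the same population. RR is the primary efficacy endpoint in all populations (Section 3.5.5.1), and primary efficacy analyses use the FAS. On that reading the single-arm tests against 10% and 15% are FAS tests, and the treated counts in the sizing support it. This largely stands for those tests. It does not settle RR and DCR by category or the logistic model: these sit inside the validation step of the primary biomarker hypothesis, and no sentence assigns them to the FAS.

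A reader might infer that the SAP contradicts itself on who is evaluable, because the first Part B interim counts patients who "have either completed the first tumor re-assessment at week 12 or discontinued the study before week 12". The documents do not support that. The interim rule times one futility look, and the SAP defines evaluability separately for each purpose, as it does for dose-limiting toxicity and pharmacokinetics.

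The assumed f may also be high for NSCLC. Part F requires a life expectancy of at least 12 weeks and ECOG 0 or 1, and its first scan is planned at week 9. These facts give no rate, but they argue for caution at the upper end of the range.

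**Conclusion.** The point holds as an unresolved denominator. Followed literally, Section 3.5.4.4 removes unscanned non-responders from RR and DCR by PD-L1 category and from the logistic model. That inflates RR within a category by 1/(1-f) and biases the contrast in a direction that cannot be known in advance. No figure in the SAP is arithmetically wrong.

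A reader might go further and infer that the PD-L1-high tests exceed their 2.5% level. The documents do not establish this. It needs the scanned denominator to be applied to tests that read more naturally as FAS tests, an assumed f, and benchmarks of 10% and 15% that refer to all treated patients. Under those conditions the excess depends on the test and on f: 75 vs 15% is above 2.5% throughout the assumed range, while 32 vs 10% passes it only beyond 10%. Nor do the documents support a claim that the PD-L1 cutoff would be shifted by a given amount, because that depends on correlations they do not report.

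The text should be clarified. Confidence is medium, because the intended reading may already be the FAS.

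**What to change.** Amend Section 3.5.4.4 to state that:
- the post-treatment assessment requirement applies to Kendall tau and other tumor-volume analyses;
- RR and DCR by PD-L1 category, the response logistic model, any response-based ROC analysis and the PD-L1-high RR tests use FAS patients with a valid PD-L1 result;
- in these response analyses, a patient with no post-treatment assessment counts as a non-responder without disease control.

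Report the number of unscanned patients and the reasons by PD-L1 category. Leave any cutoff already fixed unchanged, as Section 3.5.5.4 requires for the NSCLC cohort. Enrollment is complete (Section 1.5), so for results already analyzed on the scanned set, add the FAS version as a labeled sensitivity analysis. List the change in the clinical study report, as Section 3.5 requires.

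The cost is a short text change and one table, with no new data. The reported PD-L1-high RR may be slightly lower, and patients lost for reasons unrelated to their disease will count as failures, as the FAS already does.
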